October
2025

Women Supporting Women Using Local Solutions to Improve Infant and Young Child Feeding and Care Practices in Punjab, Pakistan

STUDY PROTOCOL

Study Overview

JUSTIFICATION.

This study responds to a call by the Pakistani government and public health researchers who have identified combatting child malnutrition as a high priority for Rahim Yar Khan (RYK) district in the province of Punjab. This study will focus on the proximal causes of malnutrition (inadequate diet and infections).

GOAL.

To rehabilitate moderately malnourished children 7-23 months of age and enable mothers to sustain this healthy growth at home by changing their infant and young child feeding (IYCF), care, hygiene, and health-seeking behaviors.

PURPOSE.

The OVERALL STUDY PURPOSE is to develop and evaluate a behavior change educational program to prevent malnutrition in the province of Punjab, Pakistan. The study has two main phases: the Formative Research Phase and the Intervention Phase.

The PURPOSE OF THE FORMATIVE RESEARCH is to identify uncommon but successful (i.e. *Positive Deviant*) IYCF behaviors practiced by local mothers of well-nourished children from economically disadvantaged homes, and to develop an education program informed by these best-practices and WHO guidelines.

The PURPOSE OF THE INTERVENTION PHASE is to deliver the educational program to mothers with undernourished children in the Intervention arm of the study who are equally disadvantaged, and to evaluate its impact on the growth of children.

STUDY HYPOTHESIS.

The primary hypothesis is that a higher proportion of Index children in the intervention compared to the control group will experience an average weight gain of 400g/month in the first 4 mos of the intervention.

STUDY OBJECTIVES.

1. Understand local perceptions, experiences, and cultural norms around IYCF practices and care,
2. Discover demonstrably successful IYCF behaviours and strategies using local resources,
3. Develop and implement a culturally appropriate and context-specific intervention,
4. Evaluate the intervention using two comparisons: (a) Within the intervention group: assess Index children's growth patterns and change in household behaviours/factors relevant to IYCF (e.g., knowledge, practice, beliefs and norms). (b) Intervention vs control group: compare average weight gain of Index children and household behaviours/factors relevant to IYCF (e.g., knowledge, practice, beliefs and norms)

Research Methods

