Anthropometric Assessment. Each Index Child's weight and height will be measured at the start and end of each hearth session, and at the end of the 2-week home visits (Day 1, Day 13, Day 27 of each cycle). If, by the end of the cycle, the child has not gained at least 400g, they will be invited to repeat the cycle—up to a maximum of three cycles. Children failing to any gain weight between cycles will be referred to a public health facility for medical evaluation. Z-Scores will be calculated to quantify the child's nutritional status. Mid-Upper Arm Circumference (MUAC) will be taken to assess for wasting. During the follow-up period, the child's weight will be monitored monthly for up to six months post-intervention.

Health assessment.

Baseline health assessments will be conducted at local public health facilities within two weeks prior to the first Hearth session for participants in the treatment arm. Each Index Child will receive a full medical examination by a physician, a Hematocrit (Hb) test via finger prick, and verification and updates for routine immunizations.

All children showing "failure to thrive" (e.g., no weight gain or weight loss after a Hearth cycle) will be referred for medical assessment within five days, and accompanied by study staff.

Results of participants' health assessments will not be shared or retained by the research team. This assessment will be conducted solely to confirm that the child meets eligibility criteria and is well enough to participate in the 28-day behaviour change program. This information is sufficient for enrollment purposes, and no medical or health records beyond the anthropometric measurements will be collected, stored, or used as study data

Data collection

Data will be collected using structured tools and include:

Baseline and follow-up household surveys (at 6 months, and possibly 12 months post-intervention if funding permits): surveys will assess 24-hour food recall and indicators on feeding practices, WASH, gender roles, and health-seeking behaviour. Study survey instrument is attached to Section 9.5.

All data will first be recorded on paper and later digitized by trained personnel.

PROCEDURES FOR PARTICIPANTS IN THE CONTROL ARM

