Participants in the control group will be enrolled after staff use the Final Recruitment Screening for Control Form to confirm eligibility, and households that express interest will be invited to join. Unlike the intervention group, control participants will not undergo a health facility-based assessment at baseline, will also not participate in the 28-day behavior change practice program, and will instead continue to receive routine care from LHWs and access health services as usual.

They will participate in the baseline and follow-up household surveys (at 6 months, and possibly 12 months post-intervention if funding permits): surveys will assess 24-hour food recall and indicators on feeding practices, WASH, gender roles, and health-seeking behaviour. Study survey instrument is attached to Section 9.5.

Anthropometric Assessment. Each Index Child's weight and height will be measured at the time of baseline and endline survey. Z-Scores will be calculated to quantify the child's nutritional status. Mid-Upper Arm Circumference (MUAC) will be taken to assess for wasting. During the follow-up period, the child's weight will be monitored monthly for up to six months post-baseline.

Time to Participate

For Treatment arm:

If a household were to partake in one hearth cycle and complete the full 6-month participation we will be offering, we can estimate the total time participants would need to commit is 40 hours over a 6-month period.

- initial recruitment assessment 0.5 hours,
- consent signing 0.5 hours,
- baseline survey 1.25 hours,
- final 6-month survey 1 hour,
- anthropometric measurement 1.5 hours (0.25 hours x 6, includes measurement taken at baseline, follow-up, and final assessment).
- 28-Day Behavior Change Practice Program. Hearth Sessions Total 34.5 hours: 12 days per cycle, 2.5 hours per day, for total = 30 hrs. Home-visits during the second half of the program total of 4.5 hours (1.5 hours three time a week for two weeks),
- Health Assessment at the medical facility may take up to 1 hour for medical screening, immunization checks, and collection of baseline height and weight measurements.

If the household participates in three hearth cycles, the time the staff will spend at the family's home is estimated to be 74.5 hours.

For Control arm:

If a household were to complete the full 6-month participation, we can estimate the total time participants would need to commit is 4.75 hours.

- initial recruitment assessment 0.5 hours,

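### The study itself produces facility contact and immunization updates in the treatment arm only, so survey items on these can differ between arms without any change in health-seeking behaviour

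*Protocol*

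**What the plan says.** The Goal in the Study Overview includes "changing their infant and young child feeding (IYCF), care, hygiene, and health-seeking behaviors". Objective 4(b) reads "Intervention vs control group: compare average weight gain of Index children and household behaviours/factors relevant to IYCF". Under Data collection for the treatment arm, "surveys will assess 24-hour food recall and indicators on feeding practices, WASH, gender roles, and health-seeking behaviour", and the control-arm procedures list the same surveys at the same times.

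Facility contact is arranged differently by arm:

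- **Treatment arm, entry.** The Consent Process section sends households to the health facility for clearance, which must be in hand before Hearth begins. Under Health assessment, the visit comprises a physician examination, a finger-prick test and "verification and updates for routine immunizations". Of its purpose the protocol says "This assessment will be conducted solely to confirm that the child meets eligibility criteria" and that the child is well enough to take part.
- **Treatment arm, later.** Children with no gain or with weight loss after a Hearth cycle "will be referred for medical assessment within five days, and accompanied by study staff".
- **Control arm.** The procedures state that "control participants will not undergo a health facility-based assessment at baseline". Controls use services as usual, and no accompanied referral is described for them, although they are weighed monthly.

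The one referral provision covering both arms is for severely malnourished children (Implementation of the Intervention, Summary), with no mention of accompaniment. The text shown has no rule for treating study-arranged contacts separately in the health-seeking indicators.

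**The concern.** A survey item that records facility contact or vaccination status does not distinguish a mother who decided to seek care from one whom the study sent or escorted. Here the study does the sending in one arm only. By the protocol's own account the entry visit is an eligibility and fitness check, not a behaviour that the programme taught. A between-arm difference on such an item could therefore be reported as success on a stated goal when part of it is the study's own procedures. If the source of each contact is not asked in the survey, the analysis will have no direct way to divide the two afterwards.

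**Working it through.** The protocol gives no figure for health-seeking, so there is none to reproduce. The check has four steps.

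**1. Is the asymmetry real?** The 28-day programme overview speaks of each child having a health check, and mother criterion 8 requires agreement to a check-up, so both could be read as covering both arms. The control-arm procedures settle this: controls have no facility assessment at baseline. The accompanied referral is triggered by a Hearth cycle, which controls do not have.

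**2. When do the contacts fall?**

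- *Clearance visit.* Consent Process puts the visit within a week of the consent discussion and the baseline survey at a home visit one week later, so the visit comes first. Eligibility Assessment has the facility's confirmation sought after consent, and Obtaining Consent places consent just before the baseline survey, so the visit can also be read as coming second.
- *Accompanied referral.* Obtaining Consent puts Hearth 1 to 2 weeks (7 to 14 days) after consent. Assume back-to-back 28-day cycles and endline at about day 182. The latest referral day is start + 28 × cycle + 5. The earliest case is 7 + 28 + 5 = day 40, and the latest is 14 + 84 + 5 = day 103. These are 182 − 40 = 142 and 182 − 103 = 79 days before endline. A recall window of about 3 to 6 months, or since baseline, would catch many or all of them; a two-week window would catch none.

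**3. How large could a false endline difference be?** Let p0 be the true proportion seeking care, equal in both arms. Let f be the share of the treatment households not otherwise counted who are counted because of a study-arranged contact. The observed treatment proportion is

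p1 = p0 + f(1 − p0), so the false difference is f(1 − p0).

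The chance of a significant result favouring the intervention (two-sided 5% test, normal approximation, independent households) is

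Φ{ [ (p1 − p0) − 1.96 √(2 p̄(1 − p̄)/n) ] / √( [p0(1 − p0) + p1(1 − p1)]/n ) }, with p̄ = (p0 + p1)/2.

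Example with p0 = 0.40, f = 0.20, n = 100: p1 = 0.40 + 0.20 × 0.60 = 0.52 and p̄ = 0.46. The two standard errors are 0.0705 and 0.0700, and (0.12 − 1.96 × 0.0705)/0.0700 = −0.26, giving 0.398.

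| p0 (assumed) | f = 0.10 | f = 0.20 | f = 0.30 |
|---|---|---|---|
| 0.20 | 8 points; 0.262 | 16 points; 0.715 | 24 points; 0.959 |
| 0.40 | 6 points; 0.135 | 12 points; 0.398 | 18 points; 0.724 |
| 0.60 | 4 points; 0.084 | 8 points; 0.216 | 12 points; 0.432 |

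With no contamination the chance is 0.025. With 80 per arm (100 less 20%), the row for p0 = 0.40 becomes 0.116, 0.330 and 0.627. The 100 per arm is the protocol's figure; p0 and f are assumptions.

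**4. Which direction for a change score?** Let f differ between baseline and endline, again with no true change. The treatment arm's change is (f_end − f_base)(1 − p0), and the control arm's is 0. At p0 = 0.40:

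- visit counted at endline only (f_base = 0, f_end = 0.20): +12 points;
- visit counted at baseline only (f_base = 0.20, f_end = 0): −12 points;
- counted equally at both, as a lasting immunization status might be: 0.

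The direction thus depends on where the clearance visit falls relative to the baseline survey and on whether endline values or changes are compared.

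**The case against.** The strongest reply is that the survey instrument, attached in a section not shown, may contain no exposed item. Items on care for a recent illness, on knowledge or on intentions would be little affected, and the exact indicator definition may properly sit in the instrument or the SAP. This stands as a limit on size. It does not remove the point, because the asymmetry is set in the protocol and the source of each contact has to be collected in the field. If the instrument already asks it, only the definition and the reporting remain to be stated.

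It can also be said that Objective 4(b) does not name health-seeking. That is so. The comparison is inferred from the Goal, the identical surveys and the objective's reference to household behaviours. Further, health-seeking is taught in the Hearth and referral of non-responders belongs to the model, so some contact is legitimately programme delivery and a real change is possible. This is why both kinds of contact should be reported rather than one discarded.

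Three stronger readings are tempting and not supported:

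- *That the treatment arm would read close to 100% by design.* This needs an item and a recall window that capture the clearance visit. On the order in Consent Process, an item asking about contact since baseline would miss it.
- *That the bias always favours the intervention.* Step 4 shows that a change score can move the other way.
- *That study-visit vaccinations can never be separated, because health results are not retained.* That restriction concerns medical records. It does not prevent asking mothers, whom the survey already interviews about child health and care-seeking.

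**Conclusion.** The point holds as a possibility built into the design: items on facility contact or immunization status can differ between arms without behaviour change, and nothing in the text shown separates the two sources. An endline comparison would tend to favour the intervention; a change score could be shrunk if the clearance visit precedes the baseline survey. Under the assumed rates in the table, the false endline difference is 4 to 24 points. The actual size is unknown, since it depends on the instrument's wording and recall window and on how many children are referred. This concerns a secondary behavioural indicator. A reader might infer that it undermines the weight-gain result; it does not bear on that hypothesis.

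**What to change.** In the data-collection text for both arms, add a survey item: for each facility contact or vaccination reported at baseline and endline, ask the mother whether the study required, arranged or accompanied it. Then:

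- define the behaviour-change indicator as household-initiated care over the same recall window in both arms;
- report study-arranged contacts and vaccinations separately, as intervention delivery;
- show the all-contacts version alongside;
- reconcile Eligibility Assessment with Consent Process on whether the clearance visit precedes the baseline survey.

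The item should be in place before baseline where possible, and must be in place before endline. It relies on the mother's report, so it is compatible with the rule against retaining health results.

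The cost is one added survey item, a narrower indicator and a possibly smaller apparent effect. The household-initiated version may also understate care-seeking in the treatment arm, because a child recently seen through the study may need less care at the household's own initiative; this is why the all-contacts version is shown as well. No change to referral or clinical care is proposed.
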